APPENDIX 5. PHARMACOGENETICS

Use and Analysis of DNA

- Germ line variation may impact a subject's response to IP, susceptibility to, and severity and progression of disease. Variable response to IP may be due to genetic determinants that impact drug absorption, distribution, metabolism, and excretion; mechanism of action of the drug; disease etiology; and/or molecular subtype of the disease being treated. Therefore, where local regulations and IRB/IEC allow, a biosample may be collected for analysis from subjects.
- Samples may be analyzed for genetic variations in genes which dramatically affect the pharmacokinetics of GB004, the safety, and/or efficacy profile. Often times, a large variability in the plasma concentration–time profiles of any medicine can be linked to loss of function mutations in the drug metabolizing enzymes and/or transporters. For example, substantial efforts have been made in reducing the risk of drug–drug interactions related to cytochrome P450 enzymes and variability caused by polymorphic expression of metabolizing enzymes (eg, UGT1A1, UGT1A6, UGT2B7). The effects of single nucleotide polymorphisms (SNPs) on the PK of GB004 uncovered in the course of this study may help guide future clinical studies and regulatory review of GB004. Additional pharmacogenetic analyses may be conducted if it is hypothesized that doing so may help resolve issues with the clinical data (eg, safety and/or pharmacodynamic observations) during the study.
- The results of these analyses may be reported in a separate study summary.
- The Sponsor will store the DNA samples in a secure storage space with adequate measures to protect confidentiality.
- The samples will be retained while research on GB004 continues but no longer than 8 years or other period as per local requirements.
- The Sponsor may elect to measure the naturally occurring variation across a range of relevant pharmacogenetic markers using modern laboratory assays, eg, the ThermoFisher DMET™ Plus Solution. This assay, for example, would cover 1,936 genetic variants across 231 relevant genes, using a single array, and would include many genetic variants that cannot easily be detected using other assays, eg, SNPs and indels with secondary polymorphisms in close proximity, triallelic markers, and variants from multi-gene families. Particular emphasis would, in this case, be placed on covering the PharmaADME “Core ADME Genes” (32 genes) and PharmaADME “Core Markers” (185 variants). If the Sponsor finds it necessary, it may move beyond the PharmaADME core content to cover common and functional variants associated with the mechanism of action of GB004, hepatic detoxification pathways, and/or other markers associated with adverse drug events eg, CYP3A4 (392A>G), structural variants in transporter genes – an important pharmaceutical target eg, ABCG2 (421C>A), enrichment for mutations in absorption, distribution, metabolism, elimination (ADME) regulatory genes eg, PPARD, inclusion of many population specific markers eg, VKORC1.

APPENDIX 6. PROHIBITED MEDICATIONS

The following medications are prohibited throughout the study:

- Azathioprine
- 6-mercaptopurine
- Any per rectum therapy (eg, enemas or suppository formulations of steroids or 5-aminosalicylates) except those required for flexible sigmoidoscopy preparation
- Marketed biologic therapies for any condition such as adalimumab, infliximab, vedolizumab, rituximab, golimumab, ustekinumab
- Tofacitinib, oral cyclosporine, sirolimus, mycophenolate mofetil
- Epoetin alfa
- Cholestyramine or other drugs interfering with enterohepatic circulation
- Any investigational agent other than GB004
- Chronic NSAID use (occasional use of NSAID, acetaminophen, or aspirin up to 325 mg/day is allowed)
- Anti-diarrheal medications (eg, loperamide, diphenoxylate/atropine)
- Strong CYP3A inhibitors and/or CYP3A inducers (eg, boceprevir, cobicistat, conivaptan, danoprevir, ritonavir, elvitegravir, grapefruit juice, indinavir, itraconazole, ketoconazole, lopinavir, paritaprevir, ombitasvir, dasabuvir, posaconazole, saquinavir, telaprevir, tipranavir, troleandomycin, voriconazole, clarithromycin, diltiazem, idelalisib, nefazodone, nelfinavir, carbamazepine, enzalutamide, mitotane, phenytoin, rifampin, St. John's wort)
- Inhibitors of UGT (eg, atazanavir; oral cannabidiol [≥ 5 mg/kg/day]; elbasvir and grazoprevir; encorafenib; epirubicin; oral fluconazole; fostamatinib; glecaprevir and pibrentasvir; isavuconazole; nelfinavir; ombitasvir and paritaprevir and ritonavir and dasabuvir; pazopanib; regorafenib; valproic acid).
- Dofetilide
- Sensitive CYP2C8 substrates (eg, repaglinide, rosiglitazone, pioglitazone, loperamide).

APPENDIX 7. LIVER SAFETY – ACTIONS AND FOLLOW-UP ASSESSMENTS

Liver assessments performed as part of the standard clinical chemistry evaluations will be evaluated as specified in the SoA (Section 1.3.1 – PCP and Section 1.3.2 – OLE) and Appendix 2 (Table 5). Parameters will include ALT, AST, GGT, ALP, total bilirubin, and direct bilirubin.

For subjects with ALT or AST $\geq 2 \times$ ULN and $< 3 \times$ ULN, confirm the value within 72 hours. Contact the Sponsor's Medical Monitor (or designee) to determine if additional liver monitoring is indicated. Blood sample for pharmacokinetic (PK) analysis should also be obtained.

For liver chemistry abnormalities actions and follow-up assessments refer to Section 7.1.3, and for dose modification refer to Section 6.5.1. The criteria requiring additional liver monitoring with possible IP interruption is provided in Table 6.

Table 6: Liver Chemistry Criteria Requiring Additional Monitoring with Possible Dose Modification of Investigational Product

Criteria	Actions
ALT or AST $\geq 3 \times$ ULN and $< 5 \times$ ULN AND bilirubin $\leq 2 \times$ ULN AND without symptoms believed to be related to liver injury or hypersensitivity^a AND who can be monitored weekly for 4 weeks	
 Notify the Sponsor's Medical Monitor (or designee) within 24 hours of learning of the abnormality to discuss subject safety. “Liver Safety Laboratory Assessment” in Table 5 may be requested by the Sponsor's Medical Monitor (or designee). Confirm values within 24-48 hours via repeat laboratories (include ALT, AST, GGT, ALP, total bilirubin, direct bilirubin, and INR). If unable to obtain repeat laboratories within 24-48 hours, decision to continue or interrupt IP will be determined by the Investigator in consultation with the Sponsor's Medical Monitor (or designee). If repeat laboratories confirm that criteria are met, the dose of IP may be reduced, with approval from the Sponsor's Medical Monitor (or designee), to doses mentioned in Section 6.5.1. Subject must return weekly or more frequently for repeat liver chemistry tests (ALT, AST, GGT, ALP, total bilirubin, direct bilirubin, and INR) until the abnormalities resolve, stabilize or return to baseline. If at any time the subject meets liver chemistry interruption criteria (as specified in Table 7), then follow the instructions in “Liver Chemistry – Investigational Product Interruption Criteria” in Table 7 and in consultation with the Sponsor's Medical Monitor (or designee) initiate relevant assessment procedures.

^aNew or worsening symptoms believed to be related to liver injury (such as fatigue, nausea, vomiting, right upper quadrant pain or tenderness, or jaundice) or hypersensitivity (such as fever, rash or eosinophilia).

Table 7: Liver Chemistry Criteria Requiring Investigational Product Interruption and Additional Monitoring

Liver Chemistry – IP Interruption Criteria	
ALT/AST (single occurrence)	ALT or AST $\geq 5 \times$ ULN
ALT/AST	ALT or AST $\geq 3 \times$ ULN persists for ≥ 4 weeks
+ Bilirubin ^{a,b}	ALT or AST $\geq 3 \times$ ULN and bilirubin $> 2 \times$ ULN ($> 35\%$ direct bilirubin)
+ INR ^b	ALT or AST $\geq 3 \times$ ULN and international normalized ratio (INR) > 1.5 , if INR measured
+ Cannot Monitor	ALT or AST $\geq 3 \times$ ULN and cannot be monitored weekly for 4 weeks
+ Symptomatic ^c	ALT or AST $\geq 3 \times$ ULN associated with symptoms (new or worsening) believed to be related to liver injury or hypersensitivity
ACTIONS	

 Immediately interrupt IP. Report the event to the Sponsor's Medical Monitor (or designee) within 24 hours. Repeat liver chemistry tests (include ALT, AST, GGT, ALP, total bilirubin, direct bilirubin, and INR) and perform the Liver Safety Laboratory Assessments (Table 5) within 24 hours. If the repeat liver chemistry test confirms the criteria are met, monitor the subject until liver chemistry test abnormalities resolve, stabilize, or return to baseline after discussion with the Sponsor's Medical Monitor (or designee) (see MONITORING). Do not restart IP unless Sponsor's Medical Monitor (or designee) approval is granted. If restart is granted, IP may be restarted at modified dose (Section 6.5.1). If restart not granted, permanently discontinue IP and continue subject in the study for any protocol specified follow up assessments. Complete an SAE data collection tool if the event also met the criteria for an SAE.^b Liver imaging (ultrasound, magnetic resonance, or computerized tomography), liver biopsy, and/or specialist consultation to evaluate liver disease may be requested by the Sponsor. 	
MONITORING	
If ALT or AST $\geq 3 \times$ ULN AND bilirubin $> 2 \times$ ULN or INR > 1.5:	If ALT or AST $\geq 3 \times$ ULN AND bilirubin $\leq 2 \times$ ULN and INR ≤ 1.5:

 Monitor subject twice weekly until liver chemistry test abnormalities resolve, stabilize, or return to baseline. 	
 Monitor subjects weekly until liver chemistry abnormalities resolve, stabilize, or return to baseline.

^a Serum bilirubin fractionation should be performed if testing is available. If serum bilirubin fractionation is not immediately available, discontinue IP if ALT or AST $\geq 3 \times$ ULN **and** bilirubin $> 2 \times$ ULN. Additionally, if serum bilirubin fractionation testing is unavailable, **record the absence/presence of detectable urinary bilirubin on dipstick** which is indicative of direct bilirubin elevations suggesting liver injury.

^b All events of ALT or AST $\geq 3 \times$ ULN **and** bilirubin $> 2 \times$ ULN ($> 35\%$ direct bilirubin) or ALT or AST $\geq 3 \times$ ULN **and** INR > 1.5 may indicate severe liver injury (**possible 'Hy's Law'**) **and must be reported as an SAE (excluding studies of hepatic impairment or cirrhosis)**. The INR stated threshold value will not apply to subjects receiving anticoagulants. INR is not part of routine laboratory assessments in this study.

^c New or worsening symptoms believed to be related to liver injury (such as fatigue, nausea, vomiting, right upper quadrant pain or tenderness, or jaundice) or hypersensitivity (such as fever, rash or eosinophilia)

APPENDIX 8. INSTRUCTIONS FOR CALCULATING MAYO SCORE FOR UC DISEASE ACTIVITY CRITERIA ASSESSMENT

Table 8 provides instructions for calculating the Mayo score for assessing the predefined UC disease activity criteria at or after the PCP Week 12 visit and prior to the PCP Week 36 visit (Section 5.3) while the subject is receiving IP.

Table 8: Instructions for Calculating Mayo Score For UC Disease Activity Criteria Assessments (at or after PCP Week 12 visit and prior to PCP Week 36 visit)

Timepoint	Instructions
At PCP Week 12 visit (post endoscopy)	
• Use PCP Week 12 visit Mayo score and centrally read Endoscopic subscore
At PCP post-Week 12 visit and prior to PCP Week 36 visit	
• Use
– Updated centrally read Endoscopic subscore (unscheduled) if previous flexible sigmoidoscopy was conducted > 4 weeks prior, otherwise use PCP Week 12 centrally read Endoscopic subscore– Updated Stool frequency subscore, Rectal bleeding subscore, and PGA

Notes:

- If, after the PCP Week 12 visit and prior to the PCP Week 36 visit, the investigator becomes aware of an increase in UC disease activity outside the normal visit schedule in a subject on IP, then a subject may also be evaluated at an Unscheduled UC Disease Activity Criteria Assessment visit as specified in the SoA (Section 1.3.1).
- Endoscopic subscores will be assessed by both a central reader (who is blinded to treatment assignment, visit, and subject symptoms) and local endoscopist (who is blinded to treatment assignment). Differences between the local endoscopist and the central reader will be adjudicated by a second blinded central reader as described in the Imaging Charter.

APPENDIX 9. **GUIDANCE TO ADDRESS A PANDEMIC OR OTHER GLOBAL HEALTH EMERGENCIES AND POTENTIAL IMPACT ON THE CLINICAL STUDY**

In the occurrence of a global health emergency affecting the conduct of the ongoing study, such as the COVID-19 pandemic, study conduct may be adjusted due to subjects being in self-isolation/quarantine, limited access to public places (including hospitals) due to the risk of spreading infections, and health care professionals being committed to critical tasks.

Adjustments to the GB004-2101 protocol may be made as described below, in line with global regulatory authorities guidance in order to ensure the safety of study participants, maintain compliance with GCP, and minimize the risks to study integrity during the COVID-19 pandemic ([EMA, April 2020](#); [FDA, March 2020](#); [Health Canada, 03 April 2020](#); [MHRH, 22 April 2020](#)). Member states within the National Competent Authorities may issue their own guidance requiring country specific recommendations to be followed.

Informed Consent

- If written consent by the study subject is not possible (for example because of physical isolation due to COVID-19 or other global health emergencies), consent could be given orally by the study subject.
- Study subjects and the person obtaining consent could sign and date separate ICFs.
- In case a written informed consent cannot be obtained at the clinical site, electronic informed consent can be obtained remotely. Alternatively, the consent form may be sent to the subject or the subject's legally authorized representative by facsimile or e-mail, and the consent interview may then be conducted by telephone/teleconference when the subject or subject's legally authorized representative can read the consent form during the discussion; the subject or subject's legally authorized representative will be requested to sign and date a blank piece of paper with a written statement affirming that they agree to participate in the study.
- If re-consent is necessary for the implementation of **new urgent changes in study conduct** (mainly expected for reasons related to global health emergencies or important safety issues for other studies), alternative ways of obtaining may include contacting the study subject via phone or video-calls and obtaining oral consents, to be documented in the study subjects' medical records, supplemented with e-mail confirmation.
- The informed consent procedure is to remain compliant with the study protocol as well as local regulatory requirements. All relevant records should be archived in the investigator's site master file. A correctly signed and dated informed consent form should be obtained from the study subjects later, as soon as possible.

Study Visits and Procedures

- COVID-19 screening procedures that may be mandated by the health care system in which a clinical study is being conducted do not need to be reported as an amendment to the protocol even if done during clinical study visits. The Investigator in

consultation with the Sponsor will decide if it is in the best interest of COVID-positive subjects to remain in the study.

- In the case of missed visits due to global health emergencies (or other health pandemic) related reasons:
 - The site should make every effort to contact the study subject to confirm and document the reason for the missed visit, and at minimum evaluate AEs/SAEs, and concomitant medications in order to assess subject safety.
 - The study subject should continue to collect the daily diary responses on the eDiary.
- In order to maintain the integrity of the study, alternative methods of collecting study procedures may be considered where possible:
 - In cases where global health emergencies-related circumstances preclude a visit to the investigative site, remote visits (eg, by telemedicine or phone contact) will be allowed for relevant study procedures.
 - In certain situations, with Sponsor approval, and according to site business continuity plans, home visits may be used to collect laboratory samples and assessments as required by the protocol.
 - In certain situations, with Sponsor approval, a local laboratory may be used to collect laboratory samples as required by the protocol. Local analysis can be used for safety decisions. In addition, local laboratory can be used for study endpoints if samples drawn at the local laboratory cannot be shipped to the central laboratory.
 - Study assessments will only be conducted in a remote manner if they can be done without affecting the wellbeing of the subject during the study and with the same level of scientific integrity as assessments conducted in a physical study center.
 - Remote study assessments can be completed via online technology. The subject may interact with study personnel using online communication tools which incorporate telemedicine.
 - Serum pregnancy tests can be performed if urine pregnancy cannot be performed.
 - For flexible sigmoidoscopy assessments in the PCP at the PCP Week 12 visit, PCP Week 36 visit, Unscheduled UC Disease Activity Criteria Assessment visit(s) and Early Withdrawal from Study visit, other options such as mobile endoscopy may be considered with Sponsor's approval.
 - If a subject is unable to complete the PCP Week 12 and/or Week 36 flexible sigmoidoscopy within the required timeframe (per SoA), there is flexibility to conduct the endoscopy up to 14 days beyond the visit window for the planned Week 12 and/or Week 36 timepoint while continuing on IP (if the subjects has not previously permanently discontinued IP); in this case, an unscheduled visit will be conducted at the planned Week 12 and/or Week 36 timepoint remotely (eg, by telemedicine) to collect AEs and concomitant medication (additional IP will be

dispensed as needed); the Week 12 and/or Week 36 visit assessments will be required at the clinic within 3 days post-endoscopy.

Supply of Investigational Product

- Alternative methods of supplying IP to enrolled study subjects (eg, direct-to-patient shipment from site) may be considered where possible.
- Additional IP will not be released to the subject without an evaluation of subject safety, including protocol-required laboratory results (at a minimum hematology, clinical chemistries and pregnancy for WOCBP), and clearance communicated to the subject. Subjects must also consent for IP shipment.

Monitoring and Audits

- Certain Sponsor oversight responsibilities, such as monitoring and quality assurance activities need to be re-assessed and temporarily, alternative proportionate mechanisms of oversight may be required. On-site audits will be avoided or postponed, and if permitted under local regulations, social distancing restrictions should apply.
- Cancelling or postponing of on-site monitoring visits and extending of the period between monitoring visits will be allowed.
- To the extent on-site monitoring remains feasible, it should take into account national, local and/or organizational social distancing restrictions.
- Centralized monitoring can be considered for data acquired by electronic data capture systems (eg, eCRFs, central laboratory or ECG / imaging data, electronic patient reported outcomes, etc.) that are in place or could be put in place provides additional monitoring capabilities that can supplement and temporarily replace on-site monitoring through a remote evaluation of ongoing and/or cumulative data collected from trial sites, in a timely manner.
- Off-site monitoring can be conducted and will include phone calls, video visits, e-mails or other online tools in order to discuss the study with the investigator and site staff. Remote monitoring should be focused on review of critical study site documentation and source data. These activities could be used to get information on the clinical study progress, to exchange information on the resolution of problems, review of procedures, study subject status as well as to facilitate remote site selection and investigator training for critical study procedures.

Risk Mitigation

- The Sponsor will continually assess whether the limitations imposed by the COVID-19 public health emergency on protocol implementation pose new safety risks to study subjects, and whether it is feasible to mitigate these risks by amending study processes and/or procedures.

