PCP Procedure	Screening	Treatment Period (Placebo-Controlled)							Unscheduled UC Disease Activity Criteria Assessment visit (post Week 12 Visit)	Early Discontinuation of IP OR Early Withdrawal from Study	Follow-up (+4 weeks after last dose of IP)	Notes
		Visit 1	2	3	4, 5	6	7, 8, 9	10				
Week	-5 to -1 (D1)	0	2	4, 8	12	18, 24, 30	36	If needed	If needed			
Window (days)			±2	±3	±5	±5	±5			- 3/+7		
Flexible sigmoidoscopy with biopsy	X ^b				X ^c		X ^c	X ^d	X ^d			
b. Screening colonoscopy may be performed instead of flexible sigmoidoscopy if needed for surveillance. Flexible sigmoidoscopy or colonoscopy will occur within 21 days of PCP Day 1/Week 0.
 
c. Flexible sigmoidoscopy should be conducted prior to the completion of the PCP Week 12 and PCP Week 36 visits to allow time for central reading. (Refer to Appendix 9 for guidance on global health emergencies accommodation for endoscopy at the Week 12 and Week 36 visits.)
 
d. To be conducted only if prior flexible sigmoidoscopy / colonoscopy was conducted > 4 weeks before the UC Disease Activity Criteria Assessment visit or Early Withdrawal from Study visit (refer to Appendix 8)

Dispense electronic diary (eDiary)	X											

PCP Procedure	Screening	Treatment Period (Placebo-Controlled)							Unscheduled UC Disease Activity Criteria Assessment visit (post Week 12 Visit)	Early Discontinuation of IP OR Early Withdrawal from Study	Follow-up (+4 weeks after last dose of IP)	Notes
		1	2	3	4, 5	6	7, 8, 9	10				
Visit	1	2	3	4, 5	6	7, 8, 9	10	If needed	If needed			
Week	-5 to -1 (D1)	0	2	4, 8	12	18, 24, 30	36					
Window (days)			±2	±3	±5	±5	±5			- 3/+7		
Review eDiary		X	X	X	X	X	X	X	X			
Assess UC Disease Activity					X	X		X				Refer to Section 5.3, can also be evaluated at Unscheduled UC Disease Activity Criteria Assessment visit (if not during an already scheduled visit), if clinically indicated.
Review Mayo score, centrally read Endoscopic subscore, Rectal bleeding subscore, and Stool frequency score		X ^e			X		X	X				e. To be reviewed prior to randomization.
Physician's Global Assessment (PGA)	X	X	X	X	X	X	X	X	X	X		
Blood plasma sample (PK)		X ^f		Wk 4 only ^f	X ^f			X ^g	X ^g			f. Blood samples will be collected predose, and 0.5, 2, and 4 hours postdose. Timepoints are in reference to the morning dose. g. Only 1 sample will be collected.

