4.1.2. OLE (24 weeks)

Subjects may participate in the 24-week OLE if in the opinion of the Investigator they have been compliant with study procedures and:

- Completed the Week 36 visit on IP; or
- Met the predefined UC Disease Activity criteria any time after PCP Week 12 visit and prior to PCP Week 36 visit on IP (refer to Section 5.3)

Beginning at the OLE Enrollment visit, all subjects will receive GB004 480 mg BID for 24 weeks. All doses will be taken at home with food with the exception of the morning dose at the OLE Enrollment visit (if last dose of PCP IP has not been taken earlier in the day), OLE Week 2, 12 and End of OLE visit/Early termination (ET) visit where IP will be administered in the clinic, with food, after predose blood collection as specified in the SoA (Section 1.3.2 – OLE).

Subsequently, subjects will return to the clinic and be evaluated as specified in the SoA (Section 1.3.2 - OLE).

Consideration should be given to discontinuing IP for subjects who do not show clinical improvement per Investigator's judgement by OLE Week 12. Subjects who permanently discontinue IP during the OLE will be withdrawn from the study, complete the End of OLE/ET visit and will be asked to return for a Follow-up visit approximately 4 weeks after their last dose of IP to assess safety.

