5.3. UC Disease Activity Criteria

Subjects meeting the following predefined UC Disease Activity criteria at or after the PCP Week 12 visit and prior to PCP Week 36 visit on IP may enter the OLE and receive GB004 BID treatment. Refer to [Table 8](#) for Mayo score calculation instructions in [Appendix 8](#).

- A Mayo score:
 - with Endoscopic subscore ≥ 2 using the centrally read endoscopy score from the flexible sigmoidoscopy,
 - AND
 - greater than or equal to the Mayo score at the PCP Day 1/Week 0 visit

AND

- Exclusion of other causes of disease activity unrelated to underlying UC (eg, infections), at the discretion of the Investigator

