8.2. Efficacy Endpoints

[Table 3](#) below provides a summary of the statistical models/methods of primary and sensitivity analyses to be used for primary, secondary, and exploratory efficacy endpoints.

Table 3: Efficacy Endpoints and Analysis Methods

Efficacy Endpoints	CMH	Logistic Regression	ANCOVA
Primary and Secondary	Primary Analyses, Sensitivity Analyses	Sensitivity Analyses	
Exploratory			
Proportion-based	Primary Analyses		
Change from baseline			Primary Analyses

Abbreviations: ANCOVA, analysis of covariance; CMH, Cochran-Mantel Haenszel

Analyses of efficacy endpoints for the PCP Week 12 Analysis (ie, efficacy endpoints evaluated at or up to and including PCP Week 12) will be based on the ITT population, unless otherwise stated below.

Analyses of efficacy endpoints for the PCP Final Analysis involving timepoints after PCP Week 12 will be based on the subset of subjects in the ITT population who consent to version 2.0 of the protocol, unless otherwise stated below.

Further analysis population details for specific efficacy endpoints are described below.

Certain secondary and exploratory efficacy endpoints will only be evaluated in a subset of subjects in the ITT population in order to ensure that achievement of the endpoint can be attributed to study treatment and that treatment effect estimation is not affected by any potential imbalance across treatment groups with respect to subjects fully or partially meeting requirements for the endpoint at baseline. This includes the following:

- Endpoints assessing histologic remission (including mucosal healing and disease clearance) will be evaluated in the subset of subjects in the ITT population with both baseline RHI lamina propria neutrophils and neutrophils in the epithelium subscores > 0 .
- Endpoints assessing histologic response will be evaluated in the subset of subjects in the ITT population with baseline RHI score ≥ 7 .
- Endpoints assessing subjects with a Geboes score ≤ 2 will be evaluated in the subset of subjects in the ITT population with a baseline Geboes score > 2 .
- The endpoint assessing steroid-free clinical remission at PCP Week 36 will be evaluated in the subset of subjects in the ITT population with an actual stratification value of yes for systemic corticosteroid use at baseline.
- Endpoints assessing the proportion of subjects with RHI score ≤ 3 will be evaluated in the subset of subjects in the ITT population with baseline RHI score > 3 .

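### Appendix 8 Table 8 names the Week 12 endoscopic subscore as the only fallback, so a reassessment soon after a later sigmoidoscopy can score early OLE eligibility on an outdated read

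*Protocol*

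**What the plan says.** Protocol Section 5.3 lets a subject who is on investigational product move to the OLE from the Week 12 visit until before the Week 36 visit. The centrally read endoscopic subscore must be at least 2 and the Mayo score must be no lower than on Day 1. A further condition is "Exclusion of other causes of disease activity unrelated to underlying UC (eg, infections), at the discretion of the Investigator". A qualifying subject "may enter the OLE and receive GB004 BID treatment", and Section 4.1.2 opens the OLE to subjects only "if in the opinion of the Investigator they have been compliant with study procedures".

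Appendix 8 Table 8 gives the scoring. At Week 12 the Week 12 scores are used. After Week 12, stool frequency, rectal bleeding and the PGA are updated, and the endoscopic component is an updated central read "if previous flexible sigmoidoscopy was conducted > 4 weeks prior, otherwise use PCP Week 12 centrally read Endoscopic subscore".

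Note d of the Schedule of Activities (Section 1.3.1) decides when a sigmoidoscopy is done at such a visit: "To be conducted only if prior flexible sigmoidoscopy / colonoscopy was conducted > 4 weeks before the UC Disease Activity Criteria Assessment visit". The same schedule places the disease activity assessment at Weeks 12, 18, 24 and 30 and adds that it "can also be evaluated at Unscheduled UC Disease Activity Criteria Assessment visit (if not during an already scheduled visit), if clinically indicated". The Table 8 notes describe the trigger for an off-schedule visit as the case where "the investigator becomes aware of an increase in UC disease activity outside the normal visit schedule in a subject on IP".

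Neither document says to use the latest read for this decision. SAP Section 8.5.1 has rules for choosing among several endoscopic subscores, but they serve the efficacy analysis visits.

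**The concern.** The two halves of the Table 8 instruction do not point at the same thing. The condition asks how old the previous sigmoidoscopy is; the fallback names one particular sigmoidoscopy. They agree when the previous procedure is the Week 12 one, and can part once there has been an unscheduled procedure after Week 12.

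A subject can have such a procedure and stay in the placebo-controlled period, because the total Mayo score fell short or because another cause, such as infection, had to be excluded first. If that subject is reassessed within 4 weeks, note d rules out a new sigmoidoscopy and Table 8 sends the site back to Week 12. Current symptoms are then added to an old endoscopic read while a newer one is on file.

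At stake is who may leave randomised treatment early. A refusal on the wrong read keeps a worsening subject, possibly on placebo, out of the OLE for a time. A grant on the wrong read cannot be undone: SAP Section 3.1.2 stops the subject's placebo-controlled data at the first OLE dose.

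**Working it through.** The plan states no figure on this point, so there is none to reproduce. The check applies the rule as written.

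**Inputs.** Eligibility (Section 5.3): endoscopic subscore ≥ 2 and Mayo score ≥ Day 1 Mayo score. Entry Mayo score 5 to 10 (Section 5.1). Target day = 7 × week + 1 (SAP Section 3.2): Week 12 = Day 85, Week 18 = 127, Week 24 = 169, Week 30 = 211, Week 36 = 253. Visit window ±5 days (Section 1.3.1). 4 weeks = 28 days.

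**Which visits are exposed.** Consecutive assessment visits are 42 days apart on target, and at least 42 − 10 = 32 days apart within windows. Scheduled visits alone therefore never fall within 28 days of each other. The first assessment after Week 12, and any assessment more than 28 days after the last sigmoidoscopy, are scored correctly. The problem needs a sigmoidoscopy after Week 12, no crossover, and a reassessment within 28 days.

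**Two illustrations.** Both take Day 1 Mayo 7, a Week 12 sigmoidoscopy on Day 85, none between then and an unscheduled one on Day 148, and a Week 24 visit on Day 169. Since 169 − 148 = 21 days, no new procedure is allowed at Week 24.

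| | Week 12 subscore | Day 148 subscore | Other three subscores, Week 24 | Table 8 read plainly | Newest read |
|---|---|---|---|---|---|
| Wrong refusal | 1 | 2 | 5 | subscore 1 < 2: not met | 5 + 2 = 7: met |
| Wrong grant | 3 | 1 | 5 | 5 + 3 = 8: met | subscore 1 < 2: not met |

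In the first case the other subscores on Day 148 summed to 4, so the total was 4 + 2 = 6 and the subject rightly stayed in. In the second, subscore 1 fails on Day 148.

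**How the scores can combine.** Take Day 1 Mayo 5–10 (6 values), the sum of the other three subscores 0–9 (10), Week 12 subscore 0–3 (4) and later subscore 0–3 (4): 6 × 10 × 4 × 4 = 960 combinations.

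- Later subscore higher (360): 126 wrong refusals, no wrong grants. By (Week 12, later): (0,2) 27, (0,3) 33, (1,2) 27, (1,3) 33, (2,3) 6.
- Later subscore lower (360): 126 wrong grants, no wrong refusals, by the mirror image.
- Equal (240): no change.

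The decision changes in 252/960 = 26% of combinations. In 27 + 33 + 27 + 33 = 120 of the 126 in each direction, the two reads lie on opposite sides of the ≥ 2 test.

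**Timing.** A new sigmoidoscopy needs more than 28 days after Day 85, so Day 114 or later. Days 114 to 252 number 139; less the three visit days, 136. The next scheduled assessment lies within 28 days for 13 of these before Week 18, 28 before Week 24 and 28 before Week 30: 69 days.

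From those days, the time until a new procedure is allowed is scope day + 29 − assessment day: 1 to 28 days, median 17. In the refusal example it is 148 + 29 − 169 = 8 days. The Week 12 read is by then 42, 84 or 126 days old at Week 18, 24 or 30, against at most 28 days for the newer one.

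**The case against.** The best defence is that Table 8 is ambiguous and has a coherent reading. Week 12 is the only sigmoidoscopy scheduled after baseline and before this interval, so the previous procedure and the Week 12 procedure may be meant as one and the same. On that reading the Day 169 example comes out right: the Week 12 procedure is 84 days old, so the updated unscheduled read from Day 148 is used. Note d, on this view, only governs when to perform a procedure. Section 5.3 itself does not name Week 12, and sites may well apply the sensible intent.

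Much of this stands. The reading is possible and may be what was intended. It is not stated, however; Section 5.3 refers to Table 8 for the calculation, and note d speaks of any prior sigmoidoscopy or colonoscopy.

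The path is also narrow, and a reader might infer more from the counts than they carry. The 26% weights all score combinations equally and does not condition on the earlier failed assessment. The 69 of 136 days treats every day as equally likely; a procedure done within 13 days after a scheduled visit has its next scheduled assessment more than 28 days away. Neither is a rate in patients.

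A reader might also infer that a wrong grant removes the subject from the randomised comparison, or that the Week 36 results are biased. The documents support neither. Week 36 efficacy "will be based on the subset of subjects in the ITT population who consent to version 2.0 of the protocol", and a subject in that subset who crosses over stays in it. The subject is normally counted as not meeting the endpoint, through the rule on stopping treatment more than 28 days before the timepoint (SAP Section 8.1.4) or through non-responder imputation (Section 8.1.1.1). Nothing shows that the error favours one arm.

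**Conclusion.** The concern holds as a small wording fault with a real consequence: read plainly, Table 8 together with note d can decide early OLE eligibility on a superseded endoscopic read. This rests on the previous sigmoidoscopy meaning any earlier one.

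A wrong refusal requires a later subscore above the Week 12 one. It is the more plausible direction, since off-schedule assessments are prompted by worsening. It can be put right once a new procedure is allowed, at most 28 days later, and the subject meanwhile remains on randomised treatment. A wrong grant requires a later subscore below the Week 12 one and still has to pass the Investigator's judgement on other causes and compliance. If it happens, randomised treatment ends early.

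The frequency cannot be estimated, because the documents give no count of unscheduled sigmoidoscopies; it is probably small. No Week 36 effect is quantified, since the number of subjects who consented to version 2.0 is not given either. The Week 12 primary endpoint is not affected.

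**What to change.** In the Appendix 8 Table 8 row for assessments after Week 12, replace the Week 12 fallback with: *otherwise use the centrally read Endoscopic subscore from the most recent sigmoidoscopy*. This gives the right score under either reading. When the Week 12 procedure is the latest one, the result is the same as now; when a later one exists, the read used is never more than 28 days old.

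The cost is one phrase, by a clarification to sites or in the next amendment. It adds no procedures and leaves the eligibility thresholds and the 4-week interval unchanged.
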